3.3 Measurements

The effectiveness of SmartJournal in enhancing nursing home caregivers' capability, opportunity, motivation and routines related to oral care tasks will be measured by a survey questionnaire capturing components of the COM-B model [26]. Caregivers in both the intervention- and the control group will be asked to fill out the survey questionnaire three times: at baseline, 3 months and 9 months.

Effects of SmartJournal usage on nursing home residents' oral health will be assessed using the mucosal-plaque score (MPS) (21) as a primary outcome measure. MPS is comprised of a four-point plaque score (PS) and a four-point mucosal score (MS). PS = 1: no visible plaque, PS = 2: plaque is barely visible, PS = 3: moderate amount of plaque, PS = 4: large amount of plaque almost covering the whole surface of teeth. MS = 1: normal mucosa, MS = 2: mild inflammation, MS = 3: medium inflammation, MS = 4: strong inflammation. For both scores, if in doubt between 1 and 2, dental personnel are instructed to score 1. If in doubt between 3 and 4, they are instructed to score 4. The index is designed to evaluate oral health and oral hygiene in groups of individuals. This makes it a suitable index to be used when conditions

are not optimal to assess the patient's oral health. In a nursing home setting, dental personnel have limited equipment and poor light compared to an ordinary dental clinic setting. Therefore, using an index designed to be applied outside a dental clinic setting is feasible in this context. Residents in both the intervention- and the control group will have MPS assessment at three times: at baseline, 3 months and 9 months. MPS assessments will be performed by dental professionals employed at the Oral Health Center of Expertise Rogaland, Norway. Calibration will be undertaken to ensure reliability of the clinical measurements.

Effects of SmartJournal usage on documentation of oral health related issues in patient journals will be measured both quantitatively (i.e., frequency of documentation) and qualitatively (i.e., qualitative assessment of documentation) at three times throughout the project period: at baseline, 3 months and 9 months. Additional journal data shown to be associated with oral health will also be retrieved and used to describe the study sample and to be included as covariates in statistical analyses. These data include socio-demographics, medical conditions and prescribed medication.

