3.2 Design and recruitment

A pragmatic cluster randomized controlled trial (C-RCT) [34] will be employed to assess effects of SmartJournal usage as specified under study objectives. Public nursing homes located in the southern part of Rogaland county, Norway, will be recruited and randomly assigned to an intervention group and a control group. Institutions housing long-term residents will be included, while institutions with primarily short-term residents, institutions already following a specific protocol for oral care and/or participate in other comprehensive interventions are excluded. Nursing homes in the intervention group will be provided with

² NSCC: National and international collaboration arena for large and small companies, municipalities, hospitals, public organizations, user organizations, academia / R&D institutions and investors. The cluster works to develop sustainable health solutions for the future (<https://www.smartcarecluster.no/english/about-us>).

tablets containing SmartJournal, while nursing homes in the control group will continue with existing oral care routines. The intervention will last for 12 weeks. Measurements will be performed at baseline, 3 months and 9 months.

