Strategies used for recruitment of individual participants (caregivers and residents), and procedures for delivery of the intervention, will be similar to those used in the feasibility study since they proved to be successful: resource groups, comprised of heads of wards and selected health personnel, will be established at each of the included nursing homes. Meetings will be scheduled to adapt delivery of the project to each individual institutions' resources and facilities, and members of the resource groups will be assigned the task of recruiting individual participants. Written informed consent will be requested for both residents and caregivers to be enrolled in the study. Nursing home residents constitutes a vulnerable group in which many individuals may have reduced decision-making capacity. For these individuals, deputy consent will be obtained from their next of kin. Residents receiving end-of-life palliative care are excluded. Both full- and parttime nursing staff will be included. Health personnel with purely administrative tasks (i.e., heads of institutions) are excluded. Following recruitment of participants and baseline measurements, nursing homes in the intervention group will be provided with SmartJournal toolboxes and packages with oral hygiene equipment, while nursing homes in the control group will receive oral hygiene equipment packages only. The SmartJournal toolboxes include tablets with SmartJournal installed, antibacterial touchscreen wipes, flashlights for monthly oral inspections, an instruction video, an instruction book and SmartJournal information posters. The oral hygiene equipment packages include toothbrushes for permanent teeth and prosthetic devices, dental floss, interdental brushes, toothpaste and inspection mirrors. Training, follow-up and technical support for SmartJournal users will be provided by project staff employed at the Oral Health Centre of Expertise Rogaland.

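### The visually graded primary outcome is scored by employees of the centre that developed and supports SmartJournal, and nothing shown conceals the arm from them, so follow-up MPS is open to detection bias

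*Protocol*

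**What the plan says.** Section 3.3 makes MPS the primary measure of residents' oral health. It combines a four-point plaque grade and a four-point mucosal grade, with verbal anchors based on how much plaque is seen and how strong the inflammation looks. The same section concedes that equipment is limited and light is poor in a nursing home. Residents in both arms are scored at baseline, 3 months and 9 months.

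On who scores: "MPS assessments will be performed by dental professionals employed at the Oral Health Center of Expertise Rogaland, Norway".

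On safeguards: "Calibration will be undertaken to ensure reliability of the clinical measurements". For doubtful grades: "if in doubt between 1 and 2, dental personnel are instructed to score 1", and "If in doubt between 3 and 4, they are instructed to score 4".

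On the centre's other roles, section 1.1 says that its researchers developed SmartJournal in collaboration with outside institutions and professionals. Section 3.2 adds: "Training, follow-up and technical support for SmartJournal users will be provided by project staff employed at the Oral Health Centre of Expertise Rogaland".

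On allocation and timing, section 3.2 randomises whole nursing homes. "Following recruitment of participants and baseline measurements, nursing homes in the intervention group will be provided with SmartJournal toolboxes", and these include tablets and "an instruction video, an instruction book and SmartJournal information posters". Control homes receive only the oral hygiene equipment. "The intervention will last for 12 weeks".

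Section 3.5 states the hypothesis that scores will move in SmartJournal's favour.

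**The concern.** A grade judged by eye in poor light leaves room for expectation. An examiner who knows the arm and expects a benefit can grade borderline residents slightly more kindly in one arm without intending to. Because allocation is by home, learning the arm of one home reveals it for all residents examined there, 30 per home as planned in section 3.4.

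A small shift that follows the arm looks exactly like a treatment effect. Covariate adjustment, correct handling of clustering or a larger sample cannot tell the two apart, because the shift and the intervention coincide. Protection has to be built in when the examination is done, so it belongs in the protocol section that already fixes who scores and how they are calibrated.

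**Working it through.** **Step 1. The examiners' employer against the centre's other roles.**

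| Role | Who | Protocol section |
|---|---|---|
| Developed SmartJournal | Researchers at the centre, with collaborators | 1.1 |
| Trains, follows up and supports users | Project staff of the centre | 3.2 |
| Scores MPS in both arms | Dental professionals employed at the centre | 3.3 |

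The common element is the employer. No passage says that the same individuals hold two of these roles, and none says that they must not.

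**Step 2. What each stated safeguard does.**

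- Calibration brings examiners into agreement with one another. It does not prevent a shift that all of them make in one arm.
- The doubt rules settle a grade once the examiner is in doubt. They do not control whether knowledge of the arm influences that doubt.
- The coded identifiers and identification key in section 4 protect privacy. They do not mask an examiner who visits the home.

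None of these conceals the arm, and the text shown contains no statement on masking of examiners.

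**Step 3. When the arm could become known.**

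- Baseline: toolboxes come afterwards, so there are no on-site signs. The protocol does not say whether randomisation precedes baseline scoring.
- 3 months: the visit falls at about the end of the 12 weeks. Tablets or posters may still be in view, which is plausible but not documented.
- 9 months: about six months after the intervention ends, no on-site sign is documented. Knowledge through the centre remains possible.

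**Step 4. Sensitivity illustration only.** The plan has no figure to reproduce here. This step shows how a given shift would act; it does not estimate the bias.

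Inputs from section 3.4: 12 homes (6 per arm), 30 residents per home, 33% drop-out, and a planning reduction from 60% to 15% (45 points) taken from another study. Assumed: 60% with a poor score in both arms (no true effect); ICC of 0.01, 0.05 or 0.10; a grading shift f of 5, 10 or 15 points in the intervention arm; and a two-sided 5% t-test on home-level results with 10 degrees of freedom.

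- Evaluable residents per home: 30 × (1 − 0.33) = 20.1
- Effective n per arm: 6 × 20.1 / (1 + 19.1 × ICC) = 101.3, 61.7 and 41.4 for the three ICCs
- SE = √[(0.60 × 0.40 + (0.60 − f)(0.40 + f)) / effective n]. For ICC 0.05 and f = 0.10: √[(0.24 + 0.25) / 61.7] = 0.089
- Non-centrality f / SE = 0.10 / 0.089 = 1.12. The chance that a non-central t with 10 df exceeds 2.228 is 0.173

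Chance of a significant result favouring SmartJournal with no true effect (2.5% without a shift):

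| ICC | f = 5 points | f = 10 points | f = 15 points |
|---|---|---|---|
| 0.01 | 9.6% | 25.5% | 49.7% |
| 0.05 | 7.4% | 17.3% | 33.2% |
| 0.10 | 6.2% | 13.0% | 24.0% |

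With no drop-out and ICC 0.05, the figures are 8.0%, 19.8% and 38.4%. The assumed shifts are 5/45 = 11%, 10/45 = 22% and 15/45 = 33% of the planning reduction.

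**The case against.** **This argues from silence.** No passage says that examiners know the allocation or deliver the intervention, and part of the text around the contributions section is not available, so roles may be described there. This stands as a limit: the point can be made only for the text shown, and unblinded scoring is not proven. It does not remove the point, because section 3.3, which specifies the scoring, is shown and gives only calibration and doubt rules.

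**Masking may be in the SAP.** Who examines residents, and what they are told, is trial conduct. An SAP cannot mask an examination already carried out.

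**A pragmatic cluster trial cannot be blinded.** This is true of caregivers. It does not follow for examiners who visit three times, and the request is limited to what is feasible.

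**Stronger readings that the documents do not support.**

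- A reader might infer that the people who support users also score MPS. Only a shared employer is shown.
- A reader might infer that posters and tablets reveal the arm at 3 months. No passage says that they are still in place then, or in view where residents are examined.
- A reader might take the missing rule for doubt between grades 2 and 3 as the route of the bias. Section 3.4 uses MPS of 2 or more; read on a four-point scale, that cut-off lies between 1 and 2, where a rule exists.
- A reader might treat the false-positive figures as a finding. They follow from assumed shifts and ICCs and a 60% rate from another study. If MPS were the sum of two grades that each start at 1, every resident would score at least 2 and the 60% would have no meaning on that scale.
- A reader might extend the point to withholding allocation from the homes. That is a separate matter of recruitment and is not argued here.

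**Conclusion.** The concern holds in a limited form. A visually graded primary outcome is scored in both arms by employees of the centre that developed SmartJournal with collaborators and supports its users. Nothing shown conceals the arm from them or separates them from that support, and the stated safeguards address consistency only. MPS at 3 and 9 months is therefore open to detection bias.

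The size of any bias is unknown and cannot be derived from the documents. The illustration shows only that, under its assumptions, shifts well below the planning reduction would raise the false-positive chance; it carries no weight in judging how serious the point is. The conclusion rests on the nature of the grade, the shared employer, allocation by home and the absence of masking in the text shown. The point merits a change because the exposure concerns the primary outcome, cannot be repaired in analysis and can be reduced cheaply.

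**What to change.** In section 3.3:

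1. Have the 3- and 9-month MPS scored by existing centre dental staff who take no part in SmartJournal training, follow-up or support and are not told allocation.
2. Let each examiner score homes in both arms, so that differences between examiners do not coincide with the arm.
3. Keep SmartJournal material out of sight at the examination where feasible. Residents need not be moved.
4. Tell examiners no allocation before a home's baseline MPS is complete.
5. If masking cannot be kept, state that MPS assessment is unblinded and limit the conclusion accordingly.

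No visit, outcome or sample size changes. Section 3.2 already delivers toolboxes after recruitment and baseline, and Table 1 places those in quarters 1 to 2 of 2023 and the intervention from quarter 3. The cost is less flexible staffing within the centre. It assumes enough dental staff for the split, and staff numbers are not given. Some unblinding on site may remain, and the shared employer stays, so the change reduces the risk without removing it.

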3.4 Power calculations and estimation of sample size for clinical outcomes

Experiences from the feasibility study show that resident participation may comprise a challenge due to high rates of morbidity, mortality and CRB in this part of the population. Estimation of sample size is largely reproduced from Overgaard et al. [32] who also used MPS as a primary outcome variable in their study on oral health in nursing home residents. Overgaard et al. based their power calculations on reductions in $MPS \geq 2$ from 60% to 15% as reported by Hede et al. [17]. Like Overgaard et al. we assume an alpha of 0.5, a power of 80% and a 33% drop-out rate due to the residents' frail condition and a median resident time of two years. Using the programme G*Power 3 [35] for power calculations, Overgaard et al. found that at least 92 residents should be included in each group for oral health assessments. A medical statistician has been consulted to further adapt the calculations to the present study setting (taking into account the number of eligible nursing homes and residents in the southern part of Rogaland), recommending the inclusion of 12 nursing homes each with 30 residents opted for oral health assessments. Thus, a total of 360 residents will be included for oral health assessments, 180 in the intervention and control group, respectively. All eligible caregivers in the 12 included nursing homes will be invited to take part in the survey capturing components of the COM-B model as described in the Measurements section (4.2). Experiences from the feasibility study indicate that this broad inclusion strategy, along with assigning the recruitment task to members of the institutions' resource groups, foster a sense of community regarding project participation. This may, in turn, motivate institutions and individual participants to remain part of the project throughout the study period.

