3.5 Data analyses

The statistical software package SPSS (IBM) will be used for analyses of quantitative data (i.e., survey data, MPS data and frequency data from patient journals). These analyses will include descriptive statistics (to describe the samples) and statistical techniques to look for changes and differences in the study variables within and between the intervention- and the control group throughout the project period - e.g., t-tests and analysis of variance (ANOVA)

tests. We hypothesize that SmartJournal usage will lead to favorable changes in variable scores. In caregivers: increased scores on the measured COM-B components (survey data). In residents: improved oral health as measured by MPS. In patient journals: increased reporting of oral health related issues. Additionally, regression analysis may be employed to investigate associations between study variables while adjusting for potential covariates (e.g., age, gender, educational level, medical conditions and prescribed medication). NVivo (Alfasoft) will be used as a tool in content analysis of oral health-related reports in patients journals. These analyses will (qualitatively) describe potential differences and changes in such reports within and between the intervention- and the control group throughout the project period.

4. Ethics and privacy

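### Section 3.4 prints an alpha of 0.5, quotes 92 per group that its listed inputs do not yield, and does not tie its 80% power to the 12 homes randomised

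*Protocol*

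**What the plan says.** Protocol section 3.2 describes the design: "A pragmatic cluster randomized controlled trial (C-RCT) [34] will be employed to assess effects of SmartJournal usage". Nursing homes, not residents, are randomised.

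Section 3.4 introduces its calculation with "Estimation of sample size is largely reproduced from" an earlier cluster randomised trial (reference 32), which also had the mucosal-plaque score (MPS) as a primary outcome. The effect is a fall in the share of residents in the MPS ≥ 2 category, "from 60% to 15% as reported by" a further cited study. The present authors then adopt the error rates as their own: "we assume an alpha of 0.5, a power of 80% and a 33% drop-out rate". The cited trial, using G*Power, "found that at least 92 residents should be included in each group for oral health assessments".

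Finally, a medical statistician is said to have adapted this to the local setting, "recommending the inclusion of 12 nursing homes each with 30 residents opted for oral health assessments". That makes 360 residents, 180 per group. The only consideration named for this step is how many homes and residents are eligible in the region. Section 3.4 gives no ICC or design effect, and no power for the 12-home design.

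**The concern.** Three statements in one paragraph do not fit together.

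- **Alpha.** A type I error rate of 0.5 is not a usable threshold. It is stated as this trial's own assumption, and no other section of the protocol gives or corrects a significance level.
- **The 92.** A reader is led from four inputs to 92 per group, but a fall from 60% to 15% is very large and needs few residents. Something that inflates the number is not shown.
- **The 80%.** It is an input to the borrowed calculation. Set beside the final 12 × 30 design, it can be taken for the power of this trial, which it is not.

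At stake is whether a reader can tell what error rate applies and what difference 6 homes per arm can detect. The second question has some substance. The 60% to 15% figure is a reduction reported from another programme, whereas here "nursing homes in the control group will receive oral hygiene equipment packages only", so control homes also receive something. The between-group difference could be smaller than 45 points, although the protocol does not say so.

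**Working it through.** **Inputs from section 3.4:** p1 = 0.60, p2 = 0.15, power 80% (z = 0.8416), drop-out 33%, alpha printed as 0.5. Sidedness is not stated. Alpha 0.05 is the presumed intention.

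**Step 1: residents per group without clustering.** With p̄ = (0.60 + 0.15)/2 = 0.375,

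n = [zα√(2p̄(1−p̄)) + zβ√(p1(1−p1) + p2(1−p2))]² / (p1−p2)²

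Here √(2 × 0.375 × 0.625) = 0.6847, √(0.24 + 0.1275) = 0.6062, and (p1−p2)² = 0.2025.

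- Two-sided 0.05 (z = 1.960): (1.3419 + 0.5102)²/0.2025 = 16.9, so 17. With continuity correction 21.2, so 22. Fisher's exact test also needs 22 (power 0.827).
- Two-sided 0.5 (z = 0.6745): (0.4618 + 0.5102)²/0.2025 = 4.7, so 5. With continuity correction 8.5, so 9.

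**Step 2: add drop-out, n/(1−0.33).**

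| Alpha | Evaluable per group | Enrolled per group |
|---|---|---|
| two-sided 0.05 | 17 to 22 | 26 to 33 |
| one-sided 0.05 | 14 to 18 | 21 to 27 |
| two-sided 0.5 (as printed) | 5 to 9 | 8 to 14 |
| one-sided 0.5 | 2 to 5 | 3 to 8 |

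No row reaches 92. Raising power to 90% and lowering alpha to 0.005 (two-sided, continuity-corrected) gives only 62 enrolled. At two-sided 0.05 the gap is 92/33 = 2.8 to 92/26 = 3.5 times.

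**Step 3: what could explain 92.** After 33% loss, 92 × 0.67 = 61.6 are evaluable. Either of two unlisted inputs would account for this:

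- a design effect of 61.6/22 = 2.8 to 61.6/17 = 3.6; or
- no design effect but a smaller difference, 60% versus about 33 to 35%, that is 25 to 27 points instead of 45.

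The protocol does not allow a choice between them.

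**Step 4: power of the planned design for 60% versus 15%.** There are 6 homes per arm and m = 30 × 0.67 = 20.1 evaluable per home, so 120.6 per arm. The test is two-sided at 0.05. The ICC is assumed, because the protocol gives none. Formula: design effect = 1 + 19.1 × ICC; variance = (0.24 + 0.1275) × design effect/120.6; noncentral t on 10 df. At ICC 0.10 the design effect is 2.91, the standard error is √(0.3675 × 2.91/120.6) = 0.0942, and the noncentrality is 0.45/0.0942 = 4.78. The check is a beta-binomial simulation with 20 residents per home and a t-test on home proportions.

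| Assumed ICC | Formula | Simulation |
|---|---|---|
| 0.05 | 99.9% | 99.8% |
| 0.10 | 99.0% | 97.8% |
| 0.20 | 91.6% | 88% |
| 0.307 | 80% | 76% |

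Power reaches 80% at an ICC of about 0.31 by the formula and about 0.27 by simulation. The simulation is the safer guide here, because the formula is optimistic at high ICC.

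**The case against.** The strongest reply is that no arithmetic of this trial is wrong: 12 × 30 = 360, and 180 per arm is almost twice 92. The 92 is reported as another trial's result. That trial was cluster randomised, so an unlisted design effect is a natural explanation. The misprinted alpha drove nothing, since at 0.5 the inputs would give 8 to 14 per group. The ICC and the detectable difference may be held in a statistical analysis plan or with the consulted statistician. Much of this stands. Absent sidedness and an absent ICC are mostly omissions, and 92 cannot be called wrong in its source. What the reply does not remove is that the paragraph gives a wrong threshold as its own assumption and runs from inputs to a figure that they do not yield. A later document does not make that text right.

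Three stronger readings are tempting and not supported:

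- **That the trial is underpowered.** For 60% versus 15% the working shows the opposite over a wide range of ICC. For a smaller contrast, say an assumed 60% versus 40%, the same formula gives about 53% at an assumed ICC of 0.05. But both values are assumptions, the outcome is taken as binary, and any gain from baseline MPS is ignored. With an assumed home-level baseline correlation of 0.5 or 0.7, power would be about 65% or 81%. The figure is an illustration and not a result for this protocol.
- **That 92 reveals an ICC.** Turning the inflation of 2.8 to 3.6 into an ICC needs the cited trial's cluster size, which is not given. A smaller difference without clustering explains 92 equally well.
- **That equipment in control homes shrinks the effect.** This is possible, but it is conjecture.

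**Conclusion.** The point holds as a correction to the written justification, not to the size. The printed alpha of 0.5 is wrong as a threshold. The listed inputs fall short of 92 by a factor of about 2.8 to 3.5 at two-sided 0.05, which is beyond any choice of test or rounding, so at least one input is missing from the account. The 80% is not a statement about 6 homes per arm. This first part rests only on the protocol's figures and on reading alpha as 0.05.

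The reassurance on size rests on further assumptions: a binary outcome, equal home sizes, about 20 evaluable residents per home, and an assumed ICC no higher than about 0.27. Within them, 360 residents is adequate for 60% versus 15%.

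**What to change.** Rewrite the sample-size paragraph in section 3.4:

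1. Correct alpha to 0.05, and state that it is two-sided if that is intended.
2. State the further input behind 92 (design effect, smaller difference or other), or stop presenting 92 as following from the listed inputs.
3. Replace the carried-over 80% with the power or detectable difference for the design as fixed: 12 homes, 6 per arm, 30 enrolled and about 20 evaluable per home. Use the ICC that the consulted statistician used. If there was none, use a range clearly labelled as assumed; do not back-calculate one from 92.

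The illustrative power for 60% versus 40% should not go into the protocol. The cost is one paragraph and a query to the statistician. The 12 homes and 360 residents stay as planned.
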